5. RATIONALE FOR THE STUDY

Previous Phase 3 studies have shown that cytisine can be effective in helping smokers to stop smoking.¹⁻³ These Phase 3 studies showed that cytisine was more effective than placebo and NRT, and as effective as varenicline for smoking cessation with an excellent safety profile. These trials used cytisine manufactured by Sopharma and safety results were consistent with the safety profile reported by Sopharma. Since tobacco smoking contributes to some 9 million premature deaths each year worldwide,⁹ using cytisinicline as a smoking cessation aid could offer far more benefit with minor risks of treatment when compared to that of continued smoking.

Data from the international EAGLES trial (N= 8120) were used to assess predictors for continuous smoking abstinence outcomes from weeks 9-24.⁴ These analyses provided clear evidence that US origin was associated with lower success rates of stopping, regardless of treatment (varenicline, bupropion, or NRT). The continuous abstinence rates from 9-24 weeks in the US were 16.1%, 11.4% and 10.6% for varenicline, bupropion, or NRT, respectively, compared to 6.7% placebo treatment. The odds ratios (OR) for these treatments in the US were 2.66, 1.78, and 1.64, respectively. The lower success rate in US smokers support the view that smokers in the US may have reached a point in the tobacco epidemic such that those who continue to smoke, despite strong cultural pressures not to smoke, have particular characteristics that make it more difficult for them to stop smoking. This highlights the need for more effective treatments for treating smokers in the US.

In the ORCA-1 Trial, conducted only in the US, the study population represented highly addicted smokers who on average were 48.4 years old and had been smoking for 32 years, meaning that most of them had started smoking in their adolescent years. In addition, they had an average of 4.5 prior quit attempts with the last quit attempt approximately 3.7 years prior to entering the study and were currently smoking an average of 1 pack of 20 cigarettes a day. Although the 3 mg TID schedule for cytisinicline showed significant abstinence rates starting from the End-of-Treatment (Week 4) through Week 8 (continuous abstinence rate of 30% compared to 8% for placebo), comments from study investigators and smokers participating in the study stated that a longer treatment would have been preferred. Since the 3 mg TID schedule is a more simplified schedule with high treatment compliance and a well-tolerated safety profile, a slightly longer 6-Week 3 mg cytisinicline treatment will be evaluated as well as another 6 weeks of treatment for a total of 12 weeks.

This Phase 3 study will be the second Phase 3 to be conducted at separate sites within the US and will also evaluate the 3 mg cytisinicline TID schedule for a longer treatment duration of 6 weeks as well as repeating that duration for a total of 12 weeks treatment. All subjects will receive standard behavioral support for smoking cessation during the study. Study treatment will be blinded and the 3 study treatment arms are defined below:

- Arm A (placebo TID for 12 weeks plus behavioral support).
- Arm B (3 mg cytisinicline TID for 6 weeks followed by placebo TID for 6 weeks plus behavioral support).
- Arm C (3 mg cytisinicline TID for 12 weeks plus behavioral support).

6. STUDY OBJECTIVES

6.1. Multiple Primary Efficacy Objectives

The multiple primary objectives are based on two comparisons where study success can be based on success for either comparison:

1. Assess whether subjects randomized to Arm B (3 mg cytisinicline TID for 6 weeks followed by placebo TID for 6 weeks plus behavioral support) have a higher probability of abstinence from Week 3 to Week 6 post-randomization as compared to subjects randomized to Arm A (placebo TID plus behavioral support).
2. Assess whether subjects randomized to Arm C (3 mg cytisinicline TID for 12 weeks plus behavioral support) have a higher probability of abstinence from Week 9 to Week 12 post-randomization as compared to subjects randomized to Arm A (placebo TID plus behavioral support).

6.2. Secondary Efficacy Objectives

The analysis for secondary objectives 1 and 2 will be done only if the corresponding primary comparison passes statistical criterion.

1. Assess whether subjects randomized to Arm B (3 mg cytisinicline TID for 6 weeks followed by placebo TID for 6 weeks plus behavioral support) have a higher probability of continuous abstinence from Week 6 to Week 24 post-randomization as compared to subjects randomized to Arm A (placebo TID plus behavioral support).
2. Assess whether subjects randomized to Arm C (3 mg cytisinicline TID for 12 weeks plus behavioral support) have a higher probability of continuous abstinence from Week 12 to Week 24 post-randomization as compared to subjects randomized to Arm A (placebo TID plus behavioral support).

The analysis for secondary objective 3 will be conditional and performed only if both primary comparisons 1 and 2 pass statistical criterion.

3. Assess for a reduction in risk of relapse from Week 6 to Week 24 in subjects receiving 3 mg cytisinicline for 6 weeks and then either continue 3 mg cytisinicline from Week 6 to Week 12 (Arm C) or were switched to placebo from Week 6 to Week 12 (Arm B). Subjects not abstinent at Week 6 will be regarded as having relapsed.

6.3. Other Objectives

1. To compare arms (Arm B vs Arm A; Arm C vs Arm A) on 7-day point prevalence abstinence weekly at Week 2 to Week 12, then for Weeks 16, 20, and 24.
2. To compare arms (Arm B vs Arm A; Arm C vs Arm A) on serum cotinine levels every other week at Week 2 to Week 12, then at Weeks 16, 20, and 24.
3. To compare arms (Arm B vs Arm A; Arm C vs Arm A) on expired CO levels every week at Week 2 through Week 12, then at Weeks 16, 20, and 24.

4. To compare arms (Arm B vs Arm A; Arm C vs Arm A) on use of any non-cigarette nicotine products, including vaping during study treatment (Week 2 through Week 12) and study follow-up (Week 16 through Week 24).
5. Assess whether subjects randomized to Arm B have a higher probability of abstinence from Week 9 to Week 12 as compared to subjects randomized to Arm A (placebo).
6. Assess among the subset of subjects who achieve abstinence from Week 3 to Week 6, whether subjects randomized to Arm B have a higher probability of continuous abstinence from Week 3 to Week 24 post-randomization as compared to homologous subjects randomized to Arm A.
7. Assess among the subset of subjects who achieve abstinence from Week 3 to Week 6, whether subjects randomized to Arm C have a higher probability of continuous abstinence at Week 24 post-randomization as compared to subjects randomized to Arm B.
8. Assess among the subset of subjects who achieve abstinence from Week 9 to Week 12, whether subjects randomized to Arm C have a higher probability of continuous abstinence from Week 9 to Week 24 post-randomization as compared to homologous subjects randomized to Arm A.
9. Among subjects who achieve abstinence from Week 3 to Week 6, compare time to failure to maintain abstinence between arms (Arm B vs Arm A; Arm C vs Arm A) to Week 24.
10. To explore the magnitude of treatment effect between arms across various subgroups defined by demographic and baseline characteristics for the primary and secondary outcomes.
11. To explore potential relationships between subject-reported outcomes (eg, anxiety, depression, withdrawal symptoms, tobacco craving) and the primary and secondary outcomes.
12. To assess possible withdrawal symptoms at Week 7 in Arm B subjects who will have discontinued cytisinicline at Week 6, analyzing separately for nicotine status (eg, either smoking, abstinent, or if using other nicotine products including vaping or nicotine replacement therapy [NRT]) compared to Arms A and Arm C.

6.4. Safety Objectives

1. To evaluate the safety profile of 3 mg TID cytisinicline compared to placebo (Arm B vs Arm A; Arm C vs Arm A).
2. To compare the safety profiles of Arm B subjects versus Arm C subjects with respect to adverse events occurring after Week 6 on the study.

[figure not shown]
7. STUDY DESIGN OVERVIEW

7.1. Study Design

This will be a multi-center, double-blind, randomized, placebo-controlled, Phase 3 study conducted in male or female adults who are ≥ 18 years age, current daily cigarette smokers, intending to quit smoking, and are willing to set a quit date within 5-7 days of being randomized on the study. Study treatment must start the day after randomization such that study treatment is initiated prior to the quit date.

Subjects must meet all requirements outlined in the inclusion and exclusion criteria. Approximately 750 subjects will be randomly assigned with equal probability (1:1:1) to three arms: (Arm A, 12 weeks placebo: N=250; Arm B, 6 weeks cytisinicline followed by 6 weeks placebo: N=250; Arm C, 12 weeks of cytisinicline) as shown in the study design figure below.

Figure 2: ACH-CYT-04 (ORCA-3) Study Design Overview

This study will be conducted at approximately 15-19 clinical sites across the US. Subjects will be randomized within site, with the goal of balancing between arm allocation within clinical sites in order to minimize imbalance for the assessment of evidence of heterogeneity of effect estimates across sites. Clinical sites will be used as a stratification factor in primary analyses.

The study will be comprised of a pre-study screen, followed by 12 weeks of treatment, and post-treatment follow up visits to 24 weeks post-randomization.

Each randomized subject will receive 12 weeks of treatment using a TID dosing schedule. Determination of smoking cessation will be made from the subject's self-report of abstinence accompanied by expired carbon monoxide (CO) biochemical verification. Assessments of smoking abstinence will begin on Week 2 (Day 14±1 post-randomization) and will continue weekly during the Treatment Period, then at the Weeks 16, 20 and 24 Follow-up Period visits.

All subjects will receive concurrent smoking cessation behavioral support during the study Treatment Period (Weeks 1-12). Additional behavioral support will be provided during the Follow-up period based on issues/concerns/questions raised by the subject.

Safety assessments at clinic visits will occur on Day 7 during Week 1 and then weekly throughout the Treatment Period. Laboratory hematology and chemistry assessments will be made on Day 7, Week 6 and Week 12 during the Treatment Period. Adverse events will be monitored through the Follow-up Period. Any ongoing adverse events at Week 24 will be followed until resolved or determined to be chronic. The end of study is defined as the last follow-up visit (up to the Week 24 visit) for the last subject.

Treatment assignment unblinding for subjects will not occur until the end of the study has been reached, the database has been locked, and final study analyses have been performed, unless defined as an unblinding exception in Section [7.3.4](#).

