16.3.1. Analysis of Primary Outcome

The outcome for each arm will be the proportion of subjects classified as a success. Each of the two experimental arms will be compared separately to the control arm (Arm A) at the appropriate timeframes. All randomized subjects will be included in the comparisons according to their randomized arm (ITT analysis). The statistical significance of each comparison will be based on the odds ratio using exact computations for stratified 2x2 frequency tables and using Monte Carlo estimation if necessary. The stratifier will be clinical site, with the possibility of pooling clinical sites having a small contribution. If cytisinicline is not favored by the effect size point estimate then the comparison will be designated as not statistically significant.

The estimated common odds ratio and its exact confidence interval will be reported. In addition, the estimated odds ratio and exact confidence interval for the marginal 2x2 table across sites (unadjusted odds ratio), and the estimated difference in proportions and the associated derived exact confidence interval using the exact confidence interval on the odds ratio will be reported. The exact difference in proportion confidence interval is derived using the method of Thomas (1971 and 1977).^{18,19}

The primary comparisons will be presented in the context of a tipping point analysis.²⁰ Other supporting and sensitivity analyses challenging the results as well as analyses designed to assess homogeneity of effect are planned and described in the SAP.

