16.4. Secondary Outcome for Subjects

The secondary efficacy outcome 1 and 2 (continued biochemically verified abstinence to Week 24) for each subject is binary: success versus failure. Success is defined for the subject as having reported smoking abstinence since the last clinic visit at each clinic assessment from Week 6 (Arm B) or Week 12 (Arm C) to Week 24 with biochemical verification at each assessment. Biochemical verification will be defined by a carbon monoxide concentration in exhaled breath of less than 10 ppm. During the Follow-up Smoking Cessation Assessment Period between Weeks 12 to 24, self-report of smoking abstinence will be according to the Russell Standard.¹⁷

The secondary efficacy outcome 3 is success with respect to being without relapse at Week 24. The secondary efficacy outcome 3 (reduction in risk of relapse from Week 6 to Week 24 in Arm C vs Arm B) will be assessed in each subject (in both Arms C and B). Subjects not abstinent at Week 6 will be regarded as having relapsed.

The considerations relative to the definition of these secondary efficacy endpoints are similar. The analyses associated with these three objectives will be done as Intent-to-Treat (ITT) analyses. The statistical model used for secondary objectives will be the same statistical model used for the analysis of the primary objectives.

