16.5. Study Size

In the 2011 published TASC Phase 3 study that evaluated cytisine versus placebo in 740 primarily moderate-to-heavy smokers treated for 25 days in Poland, the sustained 6-month abstinence rate was 10.0% in the cytisinicline arm compared to 3.5% in the placebo arm ($P<0.001$). In the 2014 published Phase 3 study that evaluated cytisinicline for 25 days versus nicotine replacement therapy (NRT) for 8 weeks in 1,310 adult daily smokers in New Zealand, the continuous six-month abstinence rate was 22% in the cytisinicline arm compared to 15% in the NRT arm ($P=0.002$).

Data from the international EAGLES trial (N=8120) were used to assess predictors for continuous smoking abstinence outcomes from Weeks 9-24. These analyses provided clear evidence that US origin was associated with lower success rates of stopping, regardless of treatment (varenicline, bupropion, or NRT). The continuous abstinence rates from 9-24 weeks in the US were 16.1%, 11.4% and 10.6% for varenicline, bupropion, or NRT, respectively, compared to 6.7% (95% CI: 5.3-8.4%) for placebo treatment. The odd ratios (OR) for these treatments in the US were 2.66, 1.78, and 1.64, respectively. The lower success rate in US smokers supports the view that smokers in the US may have particular characteristics that make it more difficult for them to stop smoking.

The trial size for this study is specified as 250 subjects per arm. The assumed control arm probability of success (continued abstinence to Week 24) is 0.07 (7%). The hypothesized experimental arm minus control arm probability difference is specified as 0.12 (12 points), corresponding to a hypothesized odds ratio of 3.116 (eg, 7% for placebo vs 19% for cytisinicline treatment). The significance level to be used is adjusted from the overall type I error probability of one-sided 0.025 to one-sided 0.0125 using the Bonferroni method to control for multiplicity. The statistical operating characteristics for each comparison are illustrated using simulation of Fisher's exact test with 10,000 replicates. These specifications are consistent with 95.7% power for each comparison with, conditional on 0.07 control arm probability outcome, an odds ratio critical region of ≥ 1.83 , corresponding to a critical difference of ≥ 0.051 (7% for placebo vs 12% for cytisinicline treatment).

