8.5. Baseline Smoking and Nicotine Testing

The following baseline data related to smoking will be summarized by treatment arm for both the All Randomized Set and the Safety Set:

- Average number of cigarettes smoked per day over 7 consecutive days, as reported in the subject diary
- Expired CO (ppm) at SV1
- Expired CO (ppm) at Day 0
- Cotinine result (ng/mL) at SV1.

If nicotine metabolism ratio (NMR) testing is done at SV1 then NMR will be derived as the ratio of the results for 3-hydroxycotinine (3-OH cotinine) and cotinine (ie, 3-OH cotinine / cotinine) and summarized by treatment arm.

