8.6. Baseline Questionnaires

Questionnaire scores will be derived as described in Section [6.4.2](#).

The following will be summarized at baseline by treatment arm for both the All Randomized Set and the Safety Set:

- FTND: total score
- HADS: total score, anxiety score, depression score
- SEQ-12: internal stimuli score, external stimuli score, and total score.
- QSU-Brief: total score
- MNWS: total score.

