10.1.3. Secondary Efficacy Analysis

The three secondary efficacy objectives are stated in Section 3.2. The secondary efficacy endpoints (continuous abstinence, risk of relapse [relapse free]) are described in Section 4.1.2.

The analysis for secondary objectives 1 and 2 will be done only if the corresponding primary comparison passes statistical criterion.

Two between-arm comparisons are planned for secondary objectives 1 and 2:

- Continuous abstinence from Week 6 to Week 24: Arm B (cytisinicline 6 weeks) vs Arm A (placebo)
- Continuous abstinence from Week 12 to Week 24: Arm C (cytisinicline 12 weeks) vs Arm A (placebo)

Each continuous abstinence endpoint is binary (success, failure). Note: For the secondary analyses, smoking abstinence during the follow up period only (Week 16 to Week 24) followed the Russell Standard of allowing up to 5 cigarettes and still be regarded as abstinent/success. Each analysis will then compare the treatment arms in terms of the proportion of subjects classified as a success using the same statistical methods as described above for the primary endpoint.

The analysis for secondary objective 3 will be conditional and performed only if both primary comparisons 1 and 2 pass statistical criterion. One between-arm comparison is planned for secondary objective 3.

- Reduction in Relapse from Week 6 to Week 24: Arm C (cytisinicline 12 weeks) vs Arm B (cytisinicline 6 weeks)

This endpoint is binary (relapsed, without relapse). The treatment arms will be compared in terms of the proportion of subjects without relapse (relapse-free) using the same statistical methods as described above for the primary endpoint.

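### All five confirmatory comparisons adjust for site only; a pre-specified estimate that also adjusts for baseline smoking measures would add modest precision at almost no cost

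*Protocol*

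**What the plan says.** For the two primary comparisons (Arm B vs A and Arm C vs A), Protocol 7.1 says "Clinical sites will be used as a stratification factor in primary analyses", and Protocol 16.3.1 adds "The stratifier will be clinical site, with the possibility of pooling clinical sites having a small contribution". SAP 10.1.2 repeats this, and its PROC FREQ template contains only site, arm and success. The secondary comparisons inherit the method: Protocol 16.4 says "The statistical model used for secondary objectives will be the same statistical model used for the analysis of the primary objectives", and SAP 10.1.3 compares the arms "using the same statistical methods as described above for the primary endpoint", including Arm C vs Arm B. Alongside the common odds ratio, the plan reports an odds ratio and a difference in proportions from the table collapsed over sites. Neither is adjusted.

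The baseline measures are in SAP 8.5, which lists "Average number of cigarettes smoked per day over 7 consecutive days, as reported in the subject diary" together with expired CO and cotinine, and in SAP 8.6, which lists "FTND: total score". Both sections only summarize them by arm. The diary average is needed for Inclusion Criterion 2. FTND is completed on Day 0 according to Protocol 12.2.2, or at SV1 according to SAP 6.4.2; both visits precede dosing.

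SAP 10.1.2.1 plans effect-modification analyses on baseline attributes. SAP 10.2.9 names diary cigarettes, CO and cotinine as possible effect modifiers for the primary endpoint; its list is open, but FTND is not named. SAP 10.3 mentions multivariable models only as data-directed work.

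**The concern.** An effect-modifier analysis asks whether the arm effect differs between subgroups. It does not use the baseline measure to sharpen the overall effect estimate, and no other planned analysis does so. Randomization is stratified by site alone, so a chance imbalance in dependence is handled neither by the design nor by a planned adjusted analysis.

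If dependence or consumption predicts quitting, adjusting for it narrows the interval for the risk difference. What is at stake is some precision in all five reported effects and a little power. Arm C vs Arm B (secondary objective 3) draws attention because the documents give no power for it.

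Timing matters too. Protocol 16 requires the SAP to be final before any unblinding. An adjusted result first produced afterwards, under SAP 10.3, would carry the data-directed label.

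**Working it through.** **1. The plan's own figure.** Inputs from Protocol 16.5: "The trial size for this study is specified as 250 subjects per arm"; 7% vs 19%; one-sided 0.0125; Fisher's exact test. Odds ratio = (0.19/0.81)/(0.07/0.93) = 3.116, as stated. Enumerating all pairs of success counts gives power 95.75%, against the stated 95.7%. The figure reproduces.

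**2. Arm C vs Arm B, no power stated.** Fisher's test, 250 per arm, one-sided 0.025 (SAP 10.1.1), Arm C assumed at the planned 19%: power is 67% if Arm B is 11%, 41% if 13% and 19% if 15%.

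**3. Variance of the risk difference.** Assume one standard normal baseline score X with logit P(success) = a(arm) + βX, and write p1(X), p0(X) for the success probabilities given X in the two arms. This model and the β values are assumptions; site is left out. With N = 500 in two equal arms:

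- Unadjusted: N × Var = 2[p1(1−p1) + p0(1−p0)].
- Adjusted (efficient): N × Var = 2E[p1(X)(1−p1(X)) + p0(X)(1−p0(X))] + Var[p1(X) − p0(X)].
- Proportional fall = Var[p1(X) + p0(X)] / {2[p1(1−p1) + p0(1−p0)]}.

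Example, 7% vs 19%, β = 0.5: denominator 2(0.0651 + 0.1539) = 0.438; numerator 0.0119; fall 2.7%.

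| Rates | β = 0.3 | β = 0.5 | β = 0.8 |
|---|---|---|---|
| 7% vs 19% | 1.0% | 2.7% | 6.7% |
| 13% vs 19% | 1.2% | 3.3% | 8.0% |
| 19% vs 27% | 1.5% | 4.1% | 9.7% |

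In absolute terms, at 7% vs 19% the 95% half-width is 1.96 × √(0.438/500) = 5.8 points, and at β = 0.8 it becomes 5.8 × √(1 − 0.067) = 5.6 points. At 13% vs 19% and β = 0.8, the saving equals 250/(1 − 0.080) − 250 ≈ 22 subjects per arm.

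**4. Power.** Simulation with 250 per arm, 17 sites (the plan says 15-19), assumed site SD 0.2 on the logit scale and 12,000 replicates. The site-stratified Mantel-Haenszel test without continuity correction is compared with a logistic score test adjusting for site and X. The β values 0.3, 0.5 and 0.8 correspond to an AUC of about 0.58, 0.64 and 0.71. The β = 0 column is the apparent gain from a useless covariate; the net gain subtracts it.

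| Rates (one-sided α) | Site-only power | Raw gain at β = 0 / 0.3 / 0.5 / 0.8 (points) | Net gain at 0.3 / 0.5 / 0.8 |
|---|---|---|---|
| 7% vs 19% (0.0125) | about 97% | 0.2 / 0.2 / 0.8 / 1.1 | 0.0 / 0.6 / 0.9 |
| 11% vs 19% (0.025) | about 71-72% | 1.2 / 1.5 / 2.4 / 4.3 | 0.3 / 1.2 / 3.1 |
| 13% vs 19% (0.025) | about 45% | 1.3 / 1.8 / 2.6 / 4.5 | 0.5 / 1.3 / 3.2 |
| 15% vs 19% (0.025) | about 22% | 1.0 / 1.3 / 1.9 / 2.7 | 0.3 / 0.9 / 1.7 |

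The standard error of one power figure near 71% is √(0.71 × 0.29/12,000) = 0.4 points, so the smallest net gains cannot be told from zero.

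**5. Two reference checks.** With both arms at 15%, the adjusted large-sample test rejected 2.6% to 2.8% of the time against a nominal 2.5%. The continuity-corrected Mantel-Haenszel test, standing in for the exact test, had 3 to 5 points less power than the uncorrected version in the Arm C vs Arm B scenarios. That is as much as, or more than, the net covariate gain.

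**The case against.** The case against is strong on several points, and most of it stands.

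- No passage says that FTND or cigarettes per day predicts abstinence; the only predictor the documents report is US origin. With no prognostic value the gain is zero. FTND item 4 is itself cigarettes per day, so the two covariates overlap, and entry at 10 or more cigarettes per day narrows their range. The size above is therefore conditional on an assumption.
- The exact site-stratified test is valid and suits sparse strata. At 7%, placebo has 0.07 × 250 = 17.5 expected successes, about one per site over 17 sites.
- The baseline measures are not ignored altogether: some are named effect modifiers.

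A reader might infer that the decision test should become a covariate-adjusted logistic regression. The material does not support that. Much of the apparent gain from such a switch comes from leaving the conservative exact test rather than from the covariate. The adjusted test was slightly liberal in the check above. The Protocol Synopsis also says this trial mirrors ORCA-2 in its analyses and statistical criteria, so changing the decision test here alone would break that parallel.

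These objections do not reach a supportive adjusted estimate. It leaves the decision test and its type I error untouched.

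**Conclusion.** The omission is real but small. All five confirmatory comparisons adjust for site only, and FTND and diary cigarettes per day enter no planned estimate of the arm effect. If the two measures together have a log odds ratio of 0.3 to 0.8 per SD (assumed), adjustment lowers the variance of the risk difference by about 1% to 10%. It adds at most about 1 point of power to the placebo comparisons at 7% vs 19%, and a net 0.3 to 3 points to Arm C vs Arm B.

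Two stronger readings do not follow. The first is that the primary tests are weakened in a way that matters: at the planned effect their power is already about 96%. The second is that Arm C vs Arm B is uniquely harmed, or that adjustment would rescue it. Its larger gain mostly reflects the ceiling on the placebo comparisons. At 7% vs 15% (4,000 replicates) the raw gain there is 1.3 to 3.6 points, similar to 1.3 to 4.5 for Arm C vs Arm B. The low power of Arm C vs Arm B comes mainly from the small plausible difference at 250 per arm.

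This is an inexpensive improvement in efficiency, not the correction of an invalid analysis.

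**What to change.** Keep the site-stratified exact test as the decision test in the Hochberg steps. In Protocol 16.3.1 and SAP 10.1.2 and 10.1.3, pre-specify before unblinding a covariate-adjusted (standardized) risk difference with 95% CI for each of the five comparisons:

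- Fit a logistic model with arm, site (same pooling rule), FTND total score and diary cigarettes per day, both covariates continuous.
- Replace a missing baseline value by the overall mean.
- Predict every subject's success probability under each of the two arms, average over subjects, and take the difference.
- Name the method for the standard error, and say what is done if a site has no successes. At 7% vs 19% the expected number per site is 250 × (0.07 + 0.19)/17 ≈ 3.8, so an empty site is possible.
- Label the estimate as supportive, and make the FTND visit agree between Protocol 12.2.2 and SAP 6.4.2.

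The cost is a short protocol and SAP edit and one extra large-sample model per comparison, with no new data. The downside is that the adjusted interval may not agree exactly with the exact P value; the SAP should say that the exact test governs.
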